4.1.3 Analysis Populations

The analysis population defined for this study is as follows:

Population	Definition / Criteria	Analyses Evaluated
Randomized	All subjects randomized in induction phase regardless of whether they received study product. Any subject who receives a randomization number will be considered to have been randomized.	Protocol deviations, disposition and medical history listings
Safety	The Safety population will comprise of all randomized subjects who receive any application of the study products.	Primary endpoint, Secondary endpoint, Safety

NOTE:

- To be randomized into the challenge phase, a subject must have been already randomized in the induction phase. Therefore, the randomization status in challenge phase won't be considered to define the randomized population. Only the randomization status in induction phase will be used to define both populations.
- Please refer to [Attachment 1: List of Data Displays](#) which details the population to be used for each of the displays being generated.

This safety study is designed to evaluate cutaneous irritation (local tolerance) and sensitization potential. There are no efficacy outcomes. Therefore, analyses will be conducted only on the Safety population.

Subjects who are randomized in the study, but did not receive any application of the study products, will not be part of safety population. Exclusion of these subjects (if any) from the safety population will be reviewed during the BDRM prior to database lock and approved prior to unblinding. [Listing 16.2.3.1](#) will display the subjects excluded from analysis population of all randomized subjects.

4.2 Subject Demographics and Other Baseline Characteristics

4.2.1 Demographic Characteristics

Descriptive statistics (number of subjects [n], mean, standard deviation [SD], median, minimum and maximum for continuous variables and frequency count [n] and percentage [%] of subjects for categorical variables) will be presented for demographic variables by overall. These variables include age, gender, race, and Fitzpatrick skin type and will be presented for the Safety population ([Table 14.1.3](#)).

The Fitzpatrick scale is a numerical classification that is widely used by dermatologists to classify a person's skin type by their response to sun exposure.

Table 4-1 Fitzpatrick Skin Type

Skin Type	Sunburn and Tanning History
I	Always burns easily; never tans (pale white skin)
II	Always burns easily; tans minimally (white skin)
III	Burns moderately; tans gradually (light brown skin)
IV	Burns minimally, always tans well (moderate brown skin)
V	Rarely burns, tans profusely (dark brown skin)
VI	Never burns (deeply pigmented dark brown to black skin)

Demographic information will be listed ([Listing 16.2.4.1](#)) for all randomized subjects.

4.2.2 General Medical History

Medical history data will be listed ([Listing 16.2.4.2](#)) for all randomized subjects with start date and end date or ongoing at the start of the study.

4.2.3 Characteristics of Disease

N/A

4.3 Treatments (Study Product, Rescue Medication, other Concomitant Therapies, Compliance)

Randomization details will be listed ([Listing 16.1.7.1](#)), including the randomization number, phase, randomization date, patch cell and corresponding planned study product and actual study product received for all randomized subjects.

4.3.1 Study Product Compliance and Exposure

Product application will be conducted at study site. Any protocol deviations associated with product applications or patch adherence will be reviewed during BDRM prior to database lock.

In addition, product and patch application details will be listed ([Listing 16.2.5.3](#)) for all randomized subjects.

4.3.2 Prior and Concomitant Medication

Prior or concomitant medication taken by or administered to a subject will be recorded in the case report form. The prior and concomitant medications will be coded using an internal validated medication dictionary, GSKDrug.

Prior medication will be listed by subject, with drug name, GSK drug synonym, reason for medication, dose, frequency, route, start date, end date, and corresponding study days relative to first study product administration in the study (i.e. in the induction phase) in [Listing 16.2.5.1](#) for all randomized subjects.

Prior medications are defined as those which stopped before the start date of first study product administration in the study (i.e. in the induction phase). If the stop date is unknown or incomplete and the medication cannot be considered as stopped prior to the start date of first study product administration in the study (i.e. in the induction phase), then the medication will be considered as concomitant medication.

Concomitant medications and concomitant non-drug treatments will be listed similarly ([Listing 16.2.5.2](#)) with either ongoing or end date displayed for all randomized subjects. Concomitant medications are defined as medications that are ongoing or started on or after the start date of first study product administration in the study (i.e. in the induction phase).

Unknown dates will not be imputed, however if the start or stop date is unknown, then it will be assumed to be concomitant medication unless the partial start date or stop date indicates differently.

4.4 Analysis of Primary Objectives

4.4.1 Primary Endpoint

4.4.1.1 Primary Endpoint Definition

The primary analysis will be based on potential sensitization reactions as assessed by a dermatologist and will be conducted on the Safety population.

For each subject who presents a positive reaction (a score of '+' or greater), a blinded dermatologist will further classify the reaction as potential sensitization (or not) at the final visit and provide a narrative description of the event. The dermatologist will not be scoring the reaction.

The assessment of positive reactions as potential sensitization reactions in the challenge phase will be determined by the blinded dermatologist and reported as:

- Yes
- No

Developmental cosmetic facial serum, lotion, and cream

212383

Final Version 1.0 Statistical Reporting and Analysis plan, 16 Jul 2019

- Unable to Determine

If “Unable to Determine” is reported, it will not be counted as a potential sensitisation reaction.

The number and percentage of subjects with any potential sensitization reactions versus those without any potential sensitization reactions will be presented by product group in [Table 14.2.1](#) for safety population. In addition, the 95% exact CIs for binomial proportions using the Clopper-Pearson method will be computed for the proportion of subjects with potential sensitization reactions and will also be presented ([Table 14.2.1](#)).

Narrative description of all potential sensitization reactions will be provided in [Listing 16.2.6.1](#) for safety population.

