#### **12.2.8 Handling of Dropouts and Missing Data**

Missing data will not be replaced or imputed. Dropouts will be included in analyses up to the last assessments at the point of discontinuation.

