1.4 Sample Size Calculation

Approximately 470 healthy subjects will be screened to randomize at least 280 subjects to ensure 200 evaluable subjects complete the entire study. If no reaction is observed in 200 subjects, the 95% exact confidence interval (CI) (Clopper-Pearson method for binomial proportions) for the true rate of positive reactions (in the general population) would be [0, 1.83%].

2 Planned Analyses

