4.4.3 Handling of Missing Values/Censoring/Discontinuations

Missing data will not be replaced or imputed. Dropouts will be included in analyses up to the point of discontinuation.

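### As written, Table 14.2.1 counts subjects never challenged as having no sensitization reaction, so the primary upper confidence limit is too low whenever subjects are lost before the challenge readings

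*SAP*

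**What the plan says.** SAP 4.4.1.1 sets the population: "The primary analysis will be based on potential sensitization reactions as assessed by a dermatologist and will be conducted on the Safety population". It describes the display thus: "The number and percentage of subjects with any potential sensitization reactions versus those without any potential sensitization reactions will be presented by product group", with an exact 95% Clopper-Pearson interval. The outcome is the blinded dermatologist's classification, at the final visit, of challenge-phase reactions scored '+' or greater. A reaction that cannot be classified does not count as sensitization.

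SAP 4.1.3 defines the population: "The Safety population will comprise of all randomized subjects who receive any application of the study products". It sets challenge randomization aside: "Only the randomization status in induction phase will be used to define both populations". For individual displays it points to Attachment 1, "which details the population to be used for each of the displays being generated"; only the file name of that attachment appears in the text.

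On missing data, SAP 4.4.3 says: "Missing data will not be replaced or imputed". Protocol 12.2.8 adds: "Dropouts will be included in analyses up to the last assessments at the point of discontinuation".

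The precision statement in SAP 1.4 has a different basis: "Approximately 470 healthy subjects will be screened to randomize at least 280 subjects to ensure 200 evaluable subjects complete the entire study". The interval of 0 to 1.83% is worked out for 200 subjects. No evaluable set is defined, and SAP 4.4.1.3 plans no supportive analysis.

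**The concern.** A subject who receives one induction patch and then leaves is in the Safety population but can never show the primary outcome. The plan expects such subjects. Protocol 8.1.7 gives a challenge randomization only to those who completed induction and remain eligible, Protocol 7.1 does not replace discontinued subjects, and SAP 4.1.1 counts those not randomized to challenge.

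If these subjects are shown as free of sensitization, the denominator of a safety endpoint grows with people who were never tested, and the error favours the products. It may also be informative. Under Protocol 4.1, a subject with '++' or greater in induction, repeated at the naïve site, may be kept out of challenge at the investigator's discretion. That subject would then appear in the table as a negative.

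**Working it through.** **Who has a classification.** Three kinds of Safety subject can be set side by side:

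- Challenged, '+' or greater: the dermatologist records a classification.
- Challenged, clean skin: no classification, because none is triggered. This is a true negative.
- Never challenged: no classification, because there was nothing to read.

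Treating every absent classification as missing would drop the true negatives along with the untested. Treating every absent classification as a negative keeps the untested. Separating the last two groups needs a rule based on challenge readings, and SAP 4.4.1.1 has none. The non-missing rule in SAP 4.5.1 is written for evaluator scores under the secondary endpoint.

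**The plan's own figure.** With 0 events, the two-sided 95% Clopper-Pearson upper limit is 1 − 0.025^(1/n). For n = 200 this is 1 − 0.025^(1/200) = 1.828%, which reproduces the stated 1.83%. The one-sided version, 1 − 0.05^(1/200) = 1.487%, does not, so the two-sided form is the one in use.

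**Effect with 0 events.** Inputs: a Safety population of 280 (the planned number randomized in SAP 1.4, assuming each receives at least one application) and an assessed number m varied from 200 (the planned completers) to 280, because no loss rate is given. The table would show 1 − 0.025^(1/280) = 1.309%. The limit supported by the assessed subjects is 1 − 0.025^(1/m). The chance of 0 events in m subjects when the true rate equals 1.309% is 0.025^(m/280); it should be 2.5%.

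| Assessed m | Limit on m | Limit shown (280) | Gap, points | Rate multiplier m/280 | One-sided non-coverage |
|---|---|---|---|---|---|
| 200 | 1.83% | 1.31% | 0.52 | 0.71 | 7.2% |
| 220 | 1.66% | 1.31% | 0.35 | 0.79 | 5.5% |
| 240 | 1.53% | 1.31% | 0.22 | 0.86 | 4.2% |
| 260 | 1.41% | 1.31% | 0.10 | 0.93 | 3.3% |
| 280 | 1.31% | 1.31% | 0 | 1.00 | 2.5% |

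**Effect with 1 event.** The upper limit is the 0.975 quantile of a Beta(x + 1, n − x) distribution with x = 1. On 200 subjects the rate is 1/200 = 0.50% with upper limit 2.75%; on 240 it is 0.42% with 2.30%; on 280 it is 0.36% with 1.97%. With 0 events the rate is 0% on any denominator, so only the limit moves.

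**The case against.** The strongest reply is that SAP 4.4.3 sits under the primary objective and forbids imputation. To record a never-challenged subject as negative is in effect to impute a negative, so the rule should already remove that subject. The intent may well be that. But applied to absent classifications it would also remove the challenged subjects with clean skin, and the text does not say which readings make a subject count as observed.

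Protocol 12.2.2 offers a second reply: exclusions are settled at a blind data review before database lock. That is a place to decide the matter, but no rule for this case is given there. Attachment 1 may also carry a denominator convention, which cannot be checked. An entry naming only the Safety population would not resolve the point.

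The replies on weight stand. SAP 4.4.1.2 plans no formal test, and the documents set no pass/fail limit for the interval. All four products share one patch, so the comparison with saline is largely unaffected. Table 14.1.1 counts subjects not randomized to challenge, which lets a reader approximate the alternative denominator, though it does not correct the reported interval.

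A reader might infer that the reported limit will be 1.31% where it should be 1.83%. The documents do not support that. It needs 80 treated subjects (280 − 200) without the challenge readings, and Protocol 4.1 gives 200 as a minimum.

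**Conclusion.** The point holds for the visible text and should be fixed. The primary display is planned on a population that includes subjects who cannot show the outcome, and nothing in SAP 4.4.1.1 or 4.4.3 takes them out while keeping the true negatives.

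With no events and 280 in the Safety population, the upper limit is understated by between 0 and 0.52 percentage points as the number assessed runs from 280 down to 200. Any non-zero rate is multiplied by the assessed fraction. These figures assume that untested subjects are counted as without a reaction. Because the plan speaks of at least 280 randomized and at least 200 completing, neither end of the range is a firm bound.

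It would go too far to say that the final analysis is certain to use the wrong denominator, since an unseen convention in Attachment 1 or a decision at blind review could prevent it. It would also go too far to say that the comparison with saline is biased to any important degree.

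**What to change.** In SAP 4.4.1.1, base the Table 14.2.1 rate and Clopper-Pearson interval, for each product, on Safety subjects who received the challenge patch and have the post-removal readings through the final visit (Visit 15 in the Schedule of Activities). Apply the rule equally to reactors and non-reactors. One early reading should not suffice: classification takes place at the final visit, and the protocol summary looks for intensity that increases over time. This rule also matches the completer basis of the sample-size statement. Naming the readings by hours after patch removal would avoid the visit numbers, which differ between Protocol 4.1 and the Schedule of Activities.

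Show subjects not challenged or incompletely assessed in a separate row with reasons. Flag any '++' or greater induction score, and any challenge score of '+' or greater that has no final classification, so that no reaction disappears from view. Keep the full Safety-population rate as a supportive line.

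Record the departure from Protocol 12.2.1 and 12.2.5 in SAP Table 5-1. If Attachment 1 already fixes this denominator, stating it in 4.4.1.1 is enough.

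The cost is SAP wording, a Table 5-1 entry and minor extra programming, with no new data. The reported upper limit becomes slightly less favourable.

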4.4.1.2 Statistical Hypothesis, Model, and Method of Analysis

No formal statistical analysis is planned for primary endpoint.

4.4.1.3 Supportive Analyses

N/A

4.4.2 Secondary Variables

There are no secondary variables defined for this study. Analysis of secondary objective/endpoint variables is defined in [Section 4.5](#).

4.4.3 Handling of Missing Values/Censoring/Discontinuations

Missing data will not be replaced or imputed. Dropouts will be included in analyses up to the point of discontinuation.

4.5 Analysis of Secondary Objectives

4.5.1 Secondary Endpoint

The key secondary analysis will be based on the positive reactions scores (scores of ‘+’ or greater) as assessed using the International Contact Dermatitis Research Group (ICDRG) scale described in [Table 4-2](#) and will be conducted on the Safety population.

Any skin response at a patched site will be clinically assessed by a trained blinded evaluator using the scale recommended by ICDRG.

Table 4-2 Scoring of Patch Cells According to ICDRG

-	Negative reaction
+?	Doubtful reaction; faint erythema only
+	Weak (non-vesicular) positive reaction; erythema, infiltration and possibly Papules
++	Strong (vesicular) positive reaction; erythema, infiltration, papules and Vesicles
+++	Extreme positive reaction; bullous reaction, intense erythema and infiltration, coalescing vesicles
IR	Irritant reaction
NT	Not tested

The following order will be used to determine severity of ICDRG scores:

- “-” < “+?” < “+” < “++” < “+++”

“IR” has no impact on the severity of a score and IR can be selected by the evaluator in addition to a positive reaction. In the end possible selections will be:

- either “-”, “+?”, “+”, “++”, “+++”
- either “+?”, “+”, “++”, “+++” and “IR”
- “NT” only

The following ICDRG scores will be considered as negative reaction scores:

- “-”
- “+?”

In addition, the following ICDRG scores will be considered as positive reaction scores:

- “+”
- “++”
- “+++”

If “NT” is selected it will be handled in the same way as missing data. Only non-missing data will be considered in the determination of skin response at a patched site. If a subject discontinues prematurely, data up to the point of discontinuation will be used.

A trained, blinded evaluator will score the test sites for signs of reactions per ICDRG scale at all timepoints specified in [Section 1-1 “Schedule of Activities”](#) of the Protocol and [Table 1-1](#) of this document. The evaluator score will be considered final.

The number and percentage of subjects with each category of score will be presented by phase, visit, and product group in [Table 14.2.2](#) for Safety Population. All patch site assessments will be listed in [Listing 16.2.6.2](#).

The number and proportion of subjects with any positive reactions scores (scores of ‘+’ or greater) will be summarized in [Table 14.2.3](#) for safety population by phase and across both

phases by product group using the maximum score. The 95% exact CIs for binomial proportions using the Clopper-Pearson method will be computed in [Table 14.2.3](#) as well.

Narrative descriptions of all positive responses (scores of + or greater), in the challenge phase, will be listed ([Listing 16.2.6.1](#)) for safety population.

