## Type and Planned Number of Subjects

Healthy male and female volunteers aged 18 to 65 with Fitzpatrick skin phototype I to IV and no dermatological disorders will be enrolled into this study.

Approximately 470 healthy subjects will be screened to randomize at least 280 subjects to ensure 200 evaluable subjects complete the entire study. If no reaction is observed in 200 subjects, there is a 95% certainty that the actual rate of reaction in the wider population will be less or equal to 1.83%.

The focus of the statistical analysis will be the number of subjects potentially sensitized and evaluation of the frequency of subjects with positive reaction scores (i.e. of '+' or greater) for the investigational products.

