**Figure 4-1      Example layout of the patch on the dorsum (shown adhesive side down)**

A semi-occlusive adhesive patch with 6 cells labelled A-F will be used. Four cells (A-D) will be used in this study (1 for each test product and 1 for the saline solution). Two cells (E-F) will remain empty.

A controlled amount (0.02 mL/cm^2) of each study product will be dispensed using suitable measuring apparatus (e.g. a pipette) into the appropriate separate cell, 3 cells for each of the test products and 1 cell for the saline solution. The assignment of the study products to the cells within the patch system within each subject will be randomly assigned per the randomization schedule provided ([5.4 Randomization Criteria](#)). The sequence of the products to the cells for each subject will remain the same for the induction phase, and a different sequence will be generated for each subject for the challenge phase ([8.1.7 Randomization](#)). Once the products have been dispensed into the cells the adhesive patch will be applied to the identified dorsum site of the subject.

During the induction phase there will be a total of 9 patch applications over 3 consecutive weeks, with patches applied to the same location on alternate weekdays each week (Monday, Wednesday, and Friday).

Each patch will remain in place for 48 ( $\pm 4$ ) hours on weekdays and 72 ( $\pm 4$ ) hours on weekends. The patch will then be removed, and the area may be gently wiped with saline solution. Subjects will be instructed to rest for 15-30 minutes (maximum 1 hour) in standard room conditions (18-26°C) avoiding contact of the back area with any other surface. After 30 minutes (maximum of 1 hour), the test sites will be evaluated as per the scale in [Appendix 2](#).

A new adhesive patch with each of the products applied to the same cells per the allocation of that subject will then be reapplied to the same area on the dorsum.

*Rest Phase:*

At visit 11, after the final induction patch removal and evaluation, subjects will enter a minimum 2-week rest phase. During this time there will be no product or patch applications. Subjects will be reminded to continue to follow the [Lifestyle Considerations](#) throughout the rest phase

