**Patch Test Site Assessments:**

Any skin response at a patched site will be clinically assessed by a trained blinded evaluator using the scale recommended by the ICDRG, per [Appendix 2](#)

Assessment of the test site areas will be conducted once at baseline (Visit 2/Day 1) prior to any patch (or product) application and then a further 8 times post-baseline during the induction phase, once during the rest phase (for the final induction phase patch removal), and 4 times during the challenge phase (prior to challenge patch application (baseline) and post) by a, trained evaluator who will be blinded to the treatment sequence allocation for both the induction and challenge phases.

During the induction phase; a trained, blinded evaluator will score the test sites for signs of irritation per ICDRG scale ([Appendix 2](#)) at all time points specified in the [study schedule](#). The trained evaluator score will be considered final. The trained evaluator does not need to be medically qualified.

During the challenge phase patch test site assessment will be conducted in a 2-step process:

Step 1: A trained, blinded evaluator will score the test sites for signs of reactions per ICDRG scale ([Appendix 2](#)) at all time points specified in the [study schedule](#). The trained evaluator score will be considered final. The trained evaluator does not need to be medically qualified.

Step 2: For each subject who presents a positive reaction (a score of '+' or greater), a blinded dermatologist will further classify the reaction as potential sensitization (or not) at the final visit and provide a narrative description of the event. The dermatologist will not be scoring the

reaction. A single event may occur over multiple visits. Only one narrative should be made. The narrative must include the start and finish date of the event, a description of how the event evolves over time, any action taken, and diagnosis (potential sensitization reaction, or not, as appropriate). If a clear diagnosis cannot be made, then the dermatologist should include this in the narrative.

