If a score (per [Appendix 2](#)) of ‘++’ (Strong) or greater at any point during the induction phase is reported, the next patch will be applied to an adjacent naïve (i.e. previously untreated) site. If a score of ‘++’ (Strong) or greater occurs at the naïve site, no further patch applications will be made. Such reactive subjects will, however, progress to the challenge phase unless, in the opinion of the Investigator (or medically qualified designee), it would be unwise to do so.

The negative control (saline solution) will be used as a reference to contextualise clinical outcomes for the test products by the Sponsor after the study completes and unblinding.

Any cutaneous (dermal) irritation or sensitization reactions which occur within the patch application area and can be completely described by the scale in [Appendix 2](#) will not be recorded as AEs during the study. These responses are typical effects of occluded application of topical products. Reactions to the patch itself or the adhesive will also not be recorded as AEs.

Unexpected or unusual reactions which occur within the patch test area that cannot be completely described by the scale in [Appendix 2](#) (e.g., rash, hives) will be recorded as AEs.

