1.2 Study Objectives

The study objectives are as follows:

Objective(s)	Endpoint(s)
Primary	
To evaluate the cutaneous sensitization potential of three cosmetic facial skincare products compared to saline solution.	Proportion of subjects potentially sensitized, as assessed by a dermatologist.
Secondary	
To evaluate the cutaneous irritation potential of three cosmetic facial skincare products compared to saline solution.	Proportion of subjects with a positive reaction (score of '+' or greater) as assessed by a trained evaluator.
Safety	
To evaluate the general safety of three cosmetic facial skincare products	Frequency and severity of Adverse Events

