1.3 Treatments

The 3 test products are developmental cosmetic moisturizers (a serum, lotion, and cream), intended to be used topically by healthy individuals with dry facial skin. A fourth reference product will be used as a negative control; saline solution.

A controlled quantity (0.02 mL/cm²) of each of the study products will be applied to a cell contained within an adhesive semi-occlusive patch system. The number of cells available in the patch system will be 6, of which 4 will be used for the products and 2 will be left blank. Each of the study products will be dispensed into 4 adjacent cells, per the randomization schedule. Three cells will be used for the test products (serum, lotion, and cream) and a fourth for the negative control (saline solution). No other products will be applied to subjects enrolled in this study.

The following study products will be supplied by the Clinical Supplies Department, GlaxoSmithKline Consumer Healthcare (GSK CH):

Developmental cosmetic facial serum, lotion, and cream

212383

Final Version 1.0 Statistical Reporting and Analysis plan, 16 Jul 2019

Table 1-2 Study Products

	Test Product 1	Test Product 2	Test Product 3	Reference Product (Negative control)
Product Name	Developmental Serum	Developmental Lotion	Developmental Cream	Saline Solution: Sodium Chloride (NaCl; 0.9%)
Pack Design	40 mL pump pack	50 mL tube	50 mL tube	500ml
Product Master Formulation Code (MFC)	CCI [REDACTED]	CCI [REDACTED]	CCI [REDACTED]	N/A Commercial Product
Application Quantity	0.02 mL/cm ² Each product will be dispensed into an individual cell within the adhesive patch system according to the randomization sequence for the induction phase and the challenge phase and removed/reapplied as per study schedule.			
Route of Administration	Topical cutaneous (dermal) application via semi-occlusive adhesive patch to the dorsum.			
Application Instruction	Applied on-site by technician			

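### SAP 4.5.1 gives no interval for the irritation difference from saline and no within-subject table, although every subject wears all four products (a cheap improvement, not an error)

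*SAP*

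**What the plan says.** SAP 1.2 words the secondary objective as a comparison: "To evaluate the cutaneous irritation potential of three cosmetic facial skincare products compared to saline solution". The design is within-subject. SAP 1.3 states: "Three cells will be used for the test products (serum, lotion, and cream) and a fourth for the negative control (saline solution"; Protocol 4.1 agrees: "Four cells (A-D) will be used in this study (1 for each test product and 1 for the saline solution".

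For this endpoint, which SAP 4.5.1 labels key, the planned outputs are:

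- Table 14.2.2: counts in each score category by phase, visit and product.
- Table 14.2.3: number and proportion of subjects with any score of + or greater, for each phase and for the two combined; the SAP's wording is "phases by product group using the maximum score. The 95% exact CIs for binomial proportions using the Clopper-Pearson method will be computed in".
- Listing 16.2.6.2: all site scores.
- Listing 16.2.6.1: narratives for challenge-phase positives.

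Protocol 12.2.6 plans the same proportions and intervals. Protocol 4.1 says that saline "will be used as a reference to contextualise clinical outcomes for the test products by the Sponsor after the study completes and unblinding", but neither document names a statistic for doing so.

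**The concern.** The objective asks how each product compares with saline, and the design makes each subject their own control. The planned table describes four separate proportions. The difference from saline follows by subtraction, but its precision does not, because that depends on how many subjects reacted in both cells.

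The overlap also matters clinically. A subject whose skin reacts to patching itself may react in several cells at once (an assumption; the documents give no concordance). A product reactor whose saline cell also reacted reads differently from one whose saline cell stayed clear. Table 14.2.3 looks the same in both situations, and a reader may fall back on asking whether two separate intervals overlap, which ignores the pairing.

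**Working it through.** **Inputs from the documents.** At least 280 subjects randomized and 200 evaluable (SAP 1.4); four cells per subject (SAP 1.3); two-sided 95% Clopper-Pearson intervals (SAP 4.5.1). The documents give no irritation rate and no within-subject agreement, so every reactor count below is an assumption.

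**The plan's own figure.** For 0 of 200, the Clopper-Pearson upper limit is 1 - 0.025^(1/200) = 1.83%, matching SAP 1.4. For 0 of 280 it is 1 - 0.025^(1/280) = 1.31%. Both are one-sample statements.

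**Paired interval.** Let b be the subjects positive at the product cell only, c those positive at the saline cell only, and n the number of pairs. The Tango score interval is the set of differences D with |T(D)| <= 1.96, where

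- T(D) = (b - c - nD) / sqrt{n[2q + D(1 - D)]}
- q = [sqrt(B² - 4AC) - B] / (2A)
- A = 2n, B = -b - c + (2n - b + c)D, C = -cD(1 - D)

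**Worked case: 14 product and 6 saline reactors, n = 280.** The difference is (14 - 6)/280 = 2.86 points. The planned intervals are 2.76 to 8.25% and 0.79 to 4.61%, whatever the overlap.

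- All 6 saline reactors shared: b = 8, c = 0. At D = 0.0145, q = 0 and T = (8 - 4.06)/sqrt(280 × 0.0145 × 0.9855) = 3.94/2.00 = 1.97, so the lower limit is about +1.45. Interval: +1.45 to +5.54.
- None shared: b = 14, c = 6. At D = -0.0030, q = 0.0378 and T = (8 + 0.84)/sqrt(20.34) = 1.96, so the lower limit is -0.30. Interval: -0.30 to +6.37.

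**Range of assumed counts, n = 280 (points):**

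| Product v saline reactors | Difference | All saline reactors shared | Half shared | None shared | Narrowing, all v none |
|---|---|---|---|---|---|
| 0 v 0 | 0 | -1.35 to +1.35 | – | – | – |
| 4 v 2 | +0.71 | -0.65 to +2.57 | -1.03 to +2.79 | -1.31 to +2.99 | 25% |
| 8 v 4 | +1.43 | +0.06 to +3.61 | -0.69 to +3.98 | -1.15 to +4.30 | 35% |
| 14 v 6 | +2.86 | +1.45 to +5.54 | +0.27 to +5.97 | -0.30 to +6.37 | 39% |
| 28 v 14 | +5.00 | +3.00 to +8.22 | +1.39 to +9.03 | +0.48 to +9.74 | 44% |

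The 0 v 0 limit is 1.96²/(n + 1.96²) = 3.84/283.84 = 1.35 points, against the one-sample upper limit of 1.31%.

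**At 200 pairs.** For 20 v 10 reactors (difference 5.0 points) the planned intervals are 6.22 to 15.02% and 2.42 to 9.00%. The paired interval is 2.74 to 8.96 with all 10 shared, 0.68 to 9.88 with 5 shared, and -0.39 to 10.68 with none shared.

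**Primary endpoint at zero events in 200.** 3.84/203.84 gives ±1.88 points against 1.83%, so pairing adds almost nothing.

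**Where the pairs can be found now.** Listing 16.1.7.1 gives "patch cell and corresponding planned study product and actual study product received for all randomized subjects", and Listing 16.2.6.2 gives the scores. Protocol 4.1 schedules site assessment "once at baseline (Visit 2/Day 1) prior to any patch (or product) application and then a further 8 times post-baseline during the induction phase", then once in the rest phase and four times in challenge: 1 + 8 + 1 + 4 = 14. A full listing could hold 280 × 4 × 14 = 15,680 scores, of which 280 × 4 × 9 = 10,080 follow an induction patch.

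**The case against.** The strongest reply is that this is a preference. Protocol 1 sets out a descriptive purpose: "The focus of the statistical analysis will be the number of subjects potentially sensitized and evaluation of the frequency of subjects with positive" scores, and that sentence goes on to name the investigational products. The sample size rests on one-sample precision alone. No margin, test or decision rule against saline appears anywhere, so whether an interval crosses zero has no formal role. The only outcome the plan discusses is zero reactions, where the gain is nil, and every non-zero count above is assumed. In the n = 280 table only 8 v 4 and 14 v 6 change side of zero, and 8 v 4 does so only with complete overlap, at a lower limit of +0.06. The narrowing figures compare two extremes. If reactors are few, a reader need check only those subjects in the listings, and challenge positives have narratives as well. The SAP's list of data displays (Attachment 1) is not reproduced in the text available, so a cross-tabulation may already be planned there.

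All of this stands as a limit on the size of the point. It does not remove it. The comparative wording is the trial's own, and a 2x2 count is as descriptive as a proportion. A listing is not a summary, and for induction the SAP text offers only the listing. The statement in SAP 4.4.1.2 that no formal analysis is planned concerns the primary endpoint; SAP 4.5.1 has no counterpart.

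**Conclusion.** The point holds as an optional improvement. The SAP text reports the irritation comparison with saline as separate columns and does not use the pairing that the design provides. The gain depends entirely on the reaction counts and their overlap, neither of which the documents give. It is nil at zero reactors. At 4 v 2 and 28 v 14 both extremes lead to the same reading with respect to zero. At intermediate counts such as 14 v 6, one and the same Table 14.2.3 is compatible with paired intervals that exclude zero and with ones that include it. No conclusion or decision rule in the plan changes. The finding is limited to the SAP text, because the list of displays could not be read.

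**What to change.** In SAP 4.5.1 and Table 14.2.3, add for each test product against saline:

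- a paired 2x2 table of + or greater (yes/no) at the product cell by + or greater at the saline cell;
- the within-subject difference in proportions with a 95% paired interval, for example the Tango score interval.

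Produce these for induction, challenge and both phases together, in Safety-population subjects with non-missing scores at both cells. State the number of pairs used, since dropout and NT scores will reduce it. Label the display descriptive and give no p-values. If Attachment 1 already contains such a display, a cross-reference is enough. The same display for potential sensitization (Table 14.2.1, challenge phase) is optional and worth producing only if at least one event occurs.

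The cost is a few lines of text and a little programming on data already collected, with no extra subjects or procedures. The downside is 3 products × 3 periods = 9 intervals without multiplicity control, or 12 with the optional display, which could be over-read if the descriptive label is dropped.
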